## 3. Introduction

## 3.1. Study Rationale

LY3314814 (AZD3293) is a brain-permeable inhibitor of human Beta-site amyloid precursor protein-cleaving enzyme 1 (BACE1/β-secretase). It is being developed for the modification of the clinical course of Alzheimer's disease (AD) by slowing disease progression in patients diagnosed with early Alzheimer's Dementia (which is defined as mild cognitive impairment (MCI) due to AD and mild dementia of the AD type). The current study, I8D-MC-AZET, will enroll patients with mild dementia of the AD type.

## 3.2. Background

Alzheimer's disease is a progressive and fatal neurodegenerative disease manifested by cognitive deterioration in addition to progressive impairment of activities of daily living. Current treatments are seen as minimally effective, with only minor symptomatic improvements for a limited duration, and they do not slow the progression of the disease.

Alzheimer's disease pathology is characterized by the formation of amyloid plaques and neurofibrillary tangles. These pathologies are associated with an inflammatory response, together with loss of neurons and synapses in the neocortex, hippocampus, and other subcortical regions of the brain. Cleavage of amyloid precursor protein (APP) by proteases known as secretases ( $\beta$  and  $\gamma$ ) gives rise to the group of peptide fragments known as A $\beta$ . They are the main components of the amyloid plaques. Further, mutations or duplications of the APP gene constitute a genetic link to Familial AD. BACE1 is a type I transmembrane aspartic acid protease related to the pepsin and retroviral aspartic protease families. BACE1 cleaves APP at the  $\beta$ -secretase site, and APP is then cleaved by  $\gamma$ -secretase generating A $\beta$  peptides.

Based on its key role in the amyloid cascade, BACE1 is considered to be a promising therapeutic target for slowing disease progression in AD. BACE1 inhibitors would be expected to prevent the generation of  $A\beta$  peptides and, consequently, reduce the detrimental effects of  $A\beta$  toxicity and the progressive formation of amyloid plaques in the brain.

As a potent inhibitor of BACE1, LY3314814 is a potential disease-modifying therapy for the treatment of AD. LY3314814 has been shown to reduce  $A\beta_{1.40}$  and  $A\beta_{1.42}$  in mice, rats, guinea pigs, dogs, and humans. At sufficient exposures, LY3314814 reduces  $A\beta$  levels in the brain and cerebrospinal fluid (CSF).

Study AZET is the second Phase 3 study in the LY3314814 registration program. It will be conducted in patients with mild AD dementia.

## 3.3. Benefit/Risk Assessment

To date, no safety issues have been identified that would create an unfavorable benefit-risk balance for LY3314814. The potential benefits are not established but expectation for an effect in slowing AD progression is described above in the Section 3.2. Potential risks include but are not limited to elevated liver enzymes, QT-prolongation with overdose, skin or hair hypopigmentation, rash, retinal changes, and potential interactions with other drugs. The potential risks are monitored with scheduled labs, electrocardiograms (ECGs), skin exams, eye exams, and restrictions on some concomitant medications. More information about the known

and expected benefits, risks, serious adverse events (SAEs) and reasonably anticipated adverse events (AEs) of LY3314814 can be found in the Investigator's Brochure (IB).

# 4. Objectives and Endpoints

Table 4.1 shows the objectives and endpoints of the study.

Table 4.1. Objectives and Endpoints

Placebo-Controlled Period									
Primary Objective	Endpoints								
To test the hypothesis that LY3314814, administered orally at doses of 20 and 50 mg daily for 78 weeks, will slow the decline of AD as compared with placebo in patients with mild AD dementia	Change in the primary endpoint measure, ADAS-Cog 13 from baseline to the end of the Placebo- Controlled period								
Secondary Objectives	Endpoints								
Clinical efficacy objectives:     To evaluate the efficacy of LY3314814 on functional, clinical, and cognitive outcomes in patients with mild AD dementia at the end of the Placebo-Controlled period (week 78). The order of testing and control of Type 1 error will be prespecified with a graphical analysis as stated in the Statistical Analysis Plan.	
 
Functional Outcome Measures         
 
ADCS-iADL score
 
FAQ
 
 
 
Cognitive/Functional Outcome Measures         
 
iADRS score
 
CDR-SB
 
 
 
Clinical Outcome Measures         
 
CDR-Global Score
 
NPI
 
 
 
Cognitive Outcome Measures         
 
MMSE
 
 
 
								

 
To evaluate the relationship between treatment effect of LY3314814 and time (at points other than the end of the Placebo-Controlled period [week 78], such as week 26 and week 52). Specific time points will vary by instrument.
 
To test the hypothesis that LY3314814 will slow the rate of cognitive and functional decline associated with AD, compared with
 
	
 
ADAS-Cog13, ADCS-iADL, FAQ, CDR-SB, and iADRS
 
ADAS-Cog13, ADCS-iADL, and FAQ using a slope analysis from a repeated-measures model
 
								

 
To evaluate the efficacy of LY3314814 to prolong time in the current disease state
 
	CDR global score								
Biomarker objectives:  • To evaluate the effect of LY3314814 on CSF  Aβ PD markers  • To evaluate the effect of LY3314814 on CSF	
 
CSF Aβ1-42 and Aβ1-40 concentrations
 
CSF total tau and phosphorylated tau
 
								

 
To evaluate the effect of LY3314814 on Esimarkers of neurodegeneration
 
To evaluate the effect of LY3314814 on brain amyloid burden
 
	concentrations  • Florbetapir amyloid scan								

 
To evaluate the effect of LY3314814 on regional cerebral blood flow (rCBF)
 
To evaluate the effect of LY3314814 on brain
 
	
 
Florbetapir perfusion scan
 
F-AV-1451 Tau PET [separate addendum]
 
								

 
aggregated tau levels
 
To evaluate the effect of LY3314814 on brain metabolism
 
	FDG PET regional cerebral metabolic rate of glucose (rCMRg) [separate addendum]								

To evaluate the effect of LY3314814 on brain atrophy	Brain volumes measured by MRI (vMRI)
Pharmacokinetic objective:  • To assess the population PK of LY3314814 and metabolite AZ13569724 in patients with mild AD dementia	
 
Apparent Oral Clearance of LY3314814
 
Central Volume of Distribution of LY3314814
 
 tart Period
	T
Secondary Objectives	Endpoints
Primary analysis:  To assess if there is a significant difference in mean change from baseline on the primary outcome measure after 6 months of the prespecified Delayed-Start period  Secondary analyses:  To assess if there is a significant difference in mean change from baseline on the primary outcome measure for the Delayed-Start period at Weeks 117, 130, 143, and 156  The delayed-start analyses as outlined above will be examined at Weeks 104, 117, 130, 143 and, 156 for additional measures of cognition and function	The ADAS-Cog 13 endpoint will be evaluated for the Delayed-Start period following the approach outlined in Liu-Seifert (2015b).  • ADAS-Cog 13 at additional timepoints, following the same approach as for the primary Delayed-Start timepoint.  • MMSE, iADRS, ADCS-iADL, and FAQ
Placebo-Controlled and	d Delayed-Start Periods
Safety Objective	Endpoints
To evaluate the safety and tolerability of LY3314814 in patients with mild AD dementia	Standard safety assessments:

Abbreviations: AD = Alzheimer's disease; ADAS-Cog13 = 13-item Alzheimer's Disease Assessment Scale – Cognitive subscale; ADCS-iADL = Alzheimer's Disease Cooperative Study Activities of Daily Living Inventory instrumental items score; CDR-SB = Clinical Dementia Rating Sum of Boxes; CI = confidence interval; CSF = cerebrospinal fluid; DNA = deoxyribonucleic acid; FAQ = Functional Activities Questionnaire; FDG = Fludeoxyglucose; iADRS = integrated Alzheimer's Disease Rating Scale; MMRM = mixed-model repeated-measures; MMSE = Mini-Mental State Examination; NPI = Neuropsychiatric Inventory; PET = positron emission tomography; PK = pharmacokinetic; RBANS = Repeatable Battery for the Assessment of Neuropsychological Status; RUD-Lite = Resource Utilization in Dementia – Lite.

# 5. Study Design

## 5.1. Overall Design

Study I8D-MC-AZET (AZET) is a multicenter, randomized, parallel-group, 78-week double-blind, placebo-controlled, comparison of 2 fixed doses of LY3314814 (20 mg or 50 mg) in patients with mild AD dementia and abnormal levels of amyloid, followed by a 78-week Delayed-Start period. There are 4 treatment arms. The randomization ratio is 2:2:1:1 (LY3314814 20 mg: LY3314814 50 mg: Placebo for 78 weeks then LY3314814 20 mg; Placebo for 78 weeks then LY3314814 50 mg). The screening for this study can be done in 2 parts, if the investigator chooses, and additional details can be found in Section 2.

The purpose of the Delayed-Start period is to assess whether LY3314814 has an effect independent of acute symptomatic effects otherwise consistent with disease-modification or slowing of disease progression. The objective is to determine whether patients starting LY3314814 78 weeks later can achieve the same outcome as those starting LY3314814 at the beginning of Visit 2. The objective will be evaluated using all available data through Week 104 (that is, 6 months into the Delayed-Start period) by the time of database lock of the Placebo-Controlled treatment period.

Placebo-Controlled Treatment Period Delayed-Start Period Visit 2 to Visit 16 Visit 16 to Visit 30 LY 20 mg LY 20 mg LY 50 mg LY 50 mg LY 20 mg-Placebo Visit 1 Screening LY 50 mg-Placebo Visit 2 Week 78 Week 104 Week 156 Visit 22 Visit 30 Randomization\* Visit 16 Primary time point for delayed-start analysis

Figure 5.1 illustrates the study design.

Abbreviations: LY=LY3314814

\*At Visit 2, patients randomized to placebo in the Placebo-Controlled treatment period will also be randomly assigned to a Delayed-Start treatment group to begin at Week 78. This will be achieved by randomizing patients to one of four sequences in a randomization ratio of 2:2:1:1 (LY3314814 20 mg: LY3314814 50 mg: Placebo then LY3314814 20 mg; Placebo then LY3314814 50 mg). The primary analysis of the Placebo-Controlled treatment period will occur at Visit 16 (Week 78). The primary analysis of the Delayed-Start period will occur at Visit 22 (Week 104).

Figure 5.1. Illustration of study design for Clinical Protocol I8D-MC-AZET.

# 5.2. Number of Participants

Approximately 3800 participants will be screened to achieve 1899 randomized for an estimated total of 633 evaluable participants per treatment group (633 in combined placebo arms during

Placebo-Controlled period). If there is an assumed 25% discontinuation rate, approximately 1424 patients will complete the Placebo-Controlled period and 1139 will complete the Delayed-Start period (in which the estimated discontinuation rate is 40% over the entire 3 year study).

## 5.3. End of Study Definition

End of the trial for the Placebo-Controlled period primary outcome measure is the date of the last visit or last scheduled procedure for Visit 16 (Week 78) shown in the Schedule of Activities (Section 2) for the last patient. End of the trial for the Delayed-Start period primary outcome measure occurs simultaneously with the end of the trial for the Placebo-Controlled period but includes all available data through Visit 22 (Week 104). End of AZET study for the Delayed-Start period secondary outcomes is the date of the last visit or last scheduled procedure for Visit 30 (Week 156) shown in the Schedule of Activities (Section 2) for the last patient.

## 5.4. Scientific Rationale for Study Design

Study AZET is designed as a second Phase 3 study to be initiated after a safety interim analysis of an ongoing Phase 2/3 study [I8D-MC-AZES] in an early AD population. Study AZET will only enroll mild AD dementia patients. The study is 18 months in duration for the primary outcome of the Placebo-Controlled period. Studies of this duration, in mild AD dementia patients, are of sufficient time to detect a difference from the placebo decline rate (Liu-Seifert et al. 2015a). Following the Placebo-Controlled period, the placebo patients will take either the 20-mg or 50-mg dose of LY3314814. Allocation to placebo or drug, and dose allocation blinds are maintained for patient and site. During this Delayed-Start period, data from randomization (Visit 2) through the initial 6 months of therapy (Week 104) will be used to test whether there is a prespecified treatment effect that cannot be achieved with the later start of treatment. The time points beyond the primary analysis at 6 months of the Delayed-Start period will be analyzed upon last patient visit for Visit 30 to determine the robustness of early treatment over the full 18-month delayed-period.

## 5.5. Justification for Dose

LY3314814 is administered orally at doses of 20 and 50 mg daily and the doses were selected based on preclinical and pharmacodynamic (PD) data. The projected therapeutic dose range is based on levels of inhibition of BACE1 in the central nervous system as calculated from the multiple-ascending-dose study of CSF A $\beta$  data. It is anticipated that 20-mg and 50-mg LY3314814 doses should achieve clinically relevant CSF A $\beta$  reductions, and the projected mean exposures at those doses should be well within the range of exposures shown to be safe and well tolerated in the Phase 1 studies and ongoing Phase 2/3 study [I8D-MC-AZES]. From Phase 1 data, the 20-mg dose is predicted to provide >50% mean reduction in CSF A $\beta$ 1-42 concentrations over the dosing interval, and the 50-mg dose is predicted to provide approximately 75% reduction in CSF A $\beta$ 1-42 concentrations over the dosing interval. Thus, these 2 doses are deemed sufficient to lower CSF A $\beta$ 1-42 concentrations to a level that will lead to a demonstration of efficacy of LY3314814 in this study based on human genetic data (Jonsson et al. 2012). The pharmacokinetic (PK) variability is expected to be sufficiently low to ensure that individual

patient exposures at these doses will also not exceed the levels already demonstrated to be safe and well tolerated.

# 6. Study Population

Prospective approval of protocol deviations to enrollment criteria, also known as protocol waivers or exemptions, are not permitted.

## 6.1. Inclusion Criteria

Patients with mild AD dementia are eligible to be included in the study only if they meet all of the following criteria at screening.

### General Criteria

- [1] Provision of signed and dated informed consent form (ICF) from patient (or legal representative if required) and from study partner prior to any study-specific procedures being performed
- [2] Male or female, aged 55 to 85 years inclusive at the time of signing ICF

## **Diagnostic Criteria**

- [3] Patient must meet the National Institute on Aging (NIA) and the Alzheimer's Association (AA) (NIA-AA) criteria for probable AD dementia (McKhann et al. 2011)
- [4] Mini-Mental State Examination (MMSE) score of 20 to 26 inclusive at screening visit
- [5] For a diagnosis of mild AD dementia, patient must have a Clinical Dementia Rating (CDR) global score of 0.5 or 1, with the memory box score  $\geq$ 0.5 at screening
- [6] Florbetapir F 18 positron emission tomography (PET) or CSF  $A\beta_{1-42}$  positive by central assessor for presence of amyloid

Note: Historical amyloid PET scans can be submitted. Note that central reading vendor for this study must confirm amyloid positivity for study eligibility. If either the florbetapir PET, historical amyloid PET or CSF  $A\beta_{1:42}$  result is negative for amyloid, patient cannot retest with other diagnostic measure. If either diagnostic is attempted but can't be completed to a final result then the test may be repeated or the alternative test can be used if available.

## Contraception

- [7] Women must be postmenopausal, surgically sterile, or having infertility due to congenital anomaly. A postmenopausal woman is defined as either having an intact uterus with at least 6 months of spontaneous amenorrhea or a diagnosis of menopause prior to starting hormone replacement therapy. Surgically sterile women are defined as those who have had a hysterectomy, bilateral ovariectomy (oophorectomy), or bilateral tubal ligation.
- [8] Men with pregnant partners should use condoms from the first day of dosing until 3 months after the last dose of study treatment and abstain for 24 hours after dose administration of the florbetapir, AV-1451 or fludeoxyglucose (FDG) PET tracer.

Men with partners of childbearing potential must abstain or use condoms plus an additional effective form of contraception from the first day of dosing until 3 months after the last dose of study treatment and abstain for 24 hours after dose administration of the florbetapir, AV-1451 or FDG PET tracer. For this protocol, sexual abstinence is defined as refraining from heterosexual intercourse during the entire period of risk associated with the study treatment. True abstinence is only acceptable when it is in line with the patient's usual and preferred lifestyle.

Note: The subject may choose to use a double–barrier method of contraception. (Barrier protection methods without concomitant use of a spermicide are not an effective or acceptable method of contraception. Thus, each barrier method must include use of a spermicide [that is, condom with spermicide, diaphragm with spermicide, female condom with spermicide]. It should be noted, however, that the use of male and female condoms as a double barrier method is not considered acceptable due to the high failure rate when these barrier methods are combined).

## **Concomitant Medication Criteria**

[9] All medication dosing should be stable for at least 30 days before screening, and between screening and randomization (does not apply to medications discontinued)

### **Procedural Criteria**

- [10] Must have completed 6 years of formal education and/or have a history of academic achievement and/or employment sufficient to exclude lifelong intellectual disability
- [11] The patient must have a reliable study partner with whom he/she cohabits or has regular contact (combination of face-to-face visits/ telephone contact acceptable). If at all possible, the same study partner should be willing to participate in study visits to provide meaningful input into the rating scales administered in this study, where study partner input is required or be available by telephone and must have sufficient patient interaction. As guidance, the ability for a study partner to meet his/her expected responsibilities for this study would normally be possible when the study partner spends no less than 10 hours per week with the subject, divided over multiple days.
- [12] Patient and study partner must be able to read, write, and speak the language in which psychometric tests are provided, with acceptable visual and auditory acuity (corrected)
- [13] Study partner must be cognitively able to fulfill the requirements of the study, in the opinion of the investigator

## 6.2. Exclusion Criteria

Patients will be excluded from study enrollment if they meet any of the following criteria at screening:

### **Medical Conditions**

- [14] Significant and/or current neurological disease affecting the central nervous system, other than AD, that may affect cognition or ability to complete the study, including but not limited to, other dementias, repetitive head trauma, serious infection of the brain, Parkinson's disease, epilepsy, or cervicocranial vascular disease.
- [15] Patients with any current primary psychiatric diagnosis other than AD if, in the judgment of the investigator, the psychiatric disorder or symptom is likely to confound interpretation of drug effect, affect cognitive assessment, or affect the patient's ability to complete the study. Patients with history of schizophrenia or other chronic psychosis are excluded.
- [16] History of alcohol or drug use disorder (except tobacco use disorder) within 2 years before the screening visit
- [17] Within 1 year before the screening visit or between screening and randomization, any of the following: myocardial infarction; moderate or severe congestive heart failure, New York Heart Association class III or IV; hospitalization for, or symptoms of, unstable angina; syncope due to orthostatic hypotension or unexplained syncope; known significant structural heart disease (such as, significant valvular disease, hypertrophic cardiomyopathy); or hospitalization for arrhythmia
- [18] Congenital QT prolongation
- [19] Intermittent second- or third-degree atrioventricular (AV) heart block or AV dissociation or history of ventricular tachycardia
- [20] A corrected QT (QTcF) interval measurement >470 msec (men and women) at screening (as determined at the investigational site)
- [21] History of malignant cancer within the last 5 years
  - Note: The following is a partial list of conditions that are permissible for study entry: non-metastatic basal and/or squamous cell carcinoma of the skin, in situ cervical, or non-progressive prostate cancer
- [22] Current serious or unstable clinically important systemic illness that, in the judgment of the investigator, is likely to affect cognitive assessment, deteriorate, or affect the patient's safety or ability to complete the study, including hepatic, renal, gastroenterologic, respiratory, cardiovascular, endocrinologic, immunologic, or hematologic disorders
- [23] History of vitiligo and/or current evidence of post-inflammatory hypopigmentation
- [24] Severe drug allergy or anaphylaxis to 2 or more drugs classes
- [25] Screening magnetic resonance imaging (MRI) shows evidence of >5 microhemorrhages; prior macrohemorrhage (>1 cm³); ≥4 infarcts, evidence of cerebral contusion, encephalomalacia, space-occupying lesion with mass-effect and edema

Note: Cortical superficial siderosis is not an exclusion.

- [26] Uncontrolled hypertension, that is, supine systolic blood pressure >165 mmHg or diastolic blood pressure >95 mmHg. If an initial blood pressure reading is higher than this, an additional attempt (at this visit or on another day) could be used before excluding a patient for uncontrolled hypertension.
- [27] Known positive serologic findings for human immunodeficiency virus (HIV) antibodies. Local laws and regulations may apply to whether testing is required.
- [28] Patients with past history (suspected or confirmed) of Hepatitis B should have HBsAg testing at screening and are excluded if HBsAg is positive.
  - Patients with past history (suspected or confirmed) of Hepatitis C (resolved >6 months prior to enrollment) should have hepatitis C virus (HCV) ribonucleic acid (RNA) polymerase chain reaction (PCR) testing at screening and are excluded if HCV RNA PCR is positive.
  - Patients in high-prevalence regions may be required to have screening serology.
- [29] Any clinically important abnormality at screening, as determined by investigator, in physical or neurological examination, vital sign, ECG, or clinical laboratory test results that could be detrimental to the patient or could compromise the study
- [30] Calculated creatinine clearance <30 mL/min (Cockcroft-Gault formula; Cockcroft and Gault 1976) at screening
- [31] Alanine aminotransferase (ALT)  $\geq$ 2x the upper limit of normal (ULN) of the performing laboratory, aspartate aminotransferase (AST)  $\geq$ 2x ULN, total bilirubin  $\geq$ 1.5x ULN, or alkaline phosphatase (ALP)  $\geq$ 1.5x ULN at screening

NOTE: Patients with total bilirubin  $\ge$ 1.5 x ULN are not excluded if they meet all of the following criteria for Gilbert syndrome:

- 1. Bilirubin is predominantly indirect (unconjugated) at screening (direct bilirubin within normal limits)
- 2. Absence of liver disease
- 3. ALT, AST, and ALP ≤1x ULN at screening
- 4. Hemoglobin not significantly decreased at screening

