### 9.4.9.4. Vasogenic Edema

If a patient develops symptoms suggestive of vasogenic edema, such as headache, confusion, gait disturbance, or visual disturbance, these should be recorded as AEs and an MRI should be obtained. Study treatment should be discontinued if clinically significant symptomatic vasogenic edema, clinically significant symptomatic superficial siderosis, or clinically significant symptomatic incident microhemorrhage is seen. Following the study treatment discontinuation, the MRI scan should be repeated within 4 weeks to evaluate the status of the finding and then performed every 4 to 6 weeks (or as clinically indicated) until the finding resolves or stabilizes. Treatment with high-dose dexamethasone is to be considered, should symptoms be severe.

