#### 10.3.4. Safety Analyses

Safety will be assessed by summarizing and analyzing AEs, laboratory analytes, vital signs, MRI scans, skin and eye examinations, and ECGs during the treatment period.

Safety analyses for the Placebo-Controlled period will include comparisons between LY3314814 dose groups and placebo. All hypotheses will be tested at a 2-sided 0.05 significance level. No adjustments for multiple comparisons will be made.

Safety analyses for the Delayed-Start period will incorporate a "contextualizing cohort" developed through modeling the plausible progression of disease for a placebo treated cohort. Further details on this modeling approach and the analysis methods will be outlined in the SAP.

For analysis comparing proportion of treatment-emergent abnormalities between treatment groups for laboratory analytes, vital signs, weight, MRI scans, skin and eye examinations, and ECGs, only patients who have both a baseline observation and a postbaseline observation will be included in the analysis for each analyte or parameter, respectively.

Suicide-related thoughts and behaviors, based on the C-SSRS, will be listed by patient and visit. Only patients that show suicidal ideation/behavior will be displayed (that is, if a patient's answers are all "no" for the C-SSRS, then that patient will not be displayed). However, if a patient reported any ideation or behavior at any time point, then all their ideation and behavior will be displayed, even if not positive.

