6.13.7. Analyses of MRI Data

To evaluate any changes in MRI data following treatment, Pearson's chi-square tests will be used to compare frequencies of responses in the MRI parameters in the Placebo-Controlled period. In the Delayed-Start period, these frequencies will be summarized.

Frequencies and percentages of the following amyloid-related imaging abnormality – edema (ARIA-E, also known as vasogenic edema) and ARIA – hemorrhage (ARIA-H, also known as microhemorrhage) parameters will be summarized:

- ARIA-E:
- o Severity (questionable, mild, moderate, severe, or no presence)
- o Status compared to the previous MRI(s) (questionable, unchanged, increased, decreased, no longer present)
- ARIA-H:
- o Number of ARIA-H (1, 2 to 5, 6 to 10, >10, or no presence),
- o Baseline to endpoint changes (increase in size of pre-existing ARIA-H, increase in number of ARIA-H, no change, partial resolution, or complete resolution)

To evaluate white matter changes over time, a shift table will be created from the following categories:

- 0 = No lesions
- 1 = Focal lesions
- 2 = Beginning confluence of lesions
- 3 = Diffuse involvement of entire region

A listing of MRI data will also be presented by subject and visit across the Placebo-Controlled and Delayed-Start periods.

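### SAP 6.13.7 defines no superficial-siderosis parameter, so siderosis found on MRI is compared between arms only where it is reported as an adverse event

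*Protocol*

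**What the plan says.** Superficial siderosis is named twice, both times in the protocol.

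- **Eligibility (protocol 6.2, criterion [25]).** The screening MRI limits microhemorrhages, macrohemorrhage and infarcts, followed by "Note: Cortical superficial siderosis is not an exclusion".
- **Stopping of treatment (protocol 9.4.9.4).** After vasogenic edema, the list continues: "clinically significant symptomatic superficial siderosis, or clinically significant symptomatic incident microhemorrhage is seen". Siderosis and microhemorrhage are separate entries.

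The protocol's safety analysis (10.3.4) includes MRI in a general rule that begins "For analysis comparing proportion of treatment-emergent abnormalities between treatment groups for laboratory analytes, vital signs, weight, MRI scans" and limits the analysis to patients with a baseline and a post-baseline observation. It names no MRI parameters.

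SAP 6.13.7 names them. The test is stated as "Pearson's chi-square tests will be used to compare frequencies of responses in the MRI parameters in the Placebo-Controlled period". The ARIA-E items are severity and status against the previous scan. The second group is introduced as "hemorrhage (ARIA-H, also known as microhemorrhage) parameters will be summarized", with two items: a count, "Number of ARIA-H (1, 2 to 5, 6 to 10, >10, or no presence", and baseline-to-endpoint change. The SAP then adds: "To evaluate white matter changes over time, a shift table will be created from the following categories". A by-subject listing of MRI data covers both periods. The SAP does not mention siderosis anywhere.

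**The concern.** The protocol treats siderosis as a distinct MRI finding with a safety consequence, and some patients may already have it at baseline. Of the three findings listed in 9.4.9.4, vasogenic edema and microhemorrhage each have an MRI parameter in the SAP; siderosis has none.

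Two things are lost. New or worsened siderosis without symptoms has no assured route into any between-arm table. And where siderosis is recorded, nothing separates patients who entered with it from new cases, so even a crude count would mix prevalence with incidence. Scheduled MRI is there to detect what symptoms do not show, and for this finding the result would reach a by-subject listing at most, and only if the central read recorded it.

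**Working it through.** The plan states no siderosis figure, so there is nothing to reproduce. The check is to follow the finding through the documents.

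1. **Entry.** Allowed (criterion [25]).
2. **Scans.** Protocol Table 2.2 schedules post-baseline MRI in the Placebo-Controlled period at Week 78 or early discontinuation, the latter only if at least 24 weeks have passed since the previous scan.
3. **Central read.** Protocol 9.4.6 names ARIA-H, ARIA-E and brain volumes as vendor outputs. Siderosis is not named. The vendor's read form is not among the documents.
4. **Is siderosis inside ARIA-H?** The protocol glossary (Appendix 1) expands ARIA-H as hemosiderin deposition, which could include it, but the same entry equates ARIA-H with microhemorrhage, as SAP 6.13.7 does. The SAP categories of 1, 2 to 5, 6 to 10 and more than 10 are lesion counts, and no rule says how siderosis would be counted. If it were pooled there, it could not be told apart from microhemorrhage.
5. **Adverse-event route.** Protocol 9.4.6 sends clinically significant MRI findings that lead to a diagnosis to the pre-existing-condition or adverse-event record. SAP 6.13.2 compares treatment-emergent events, serious events and events leading to treatment discontinuation by Fisher's exact test. Siderosis that meets the 9.4.9.4 condition should arrive here. Siderosis without symptoms need not.
6. **Special-interest clusters.** Table AZET.SAP.2 names no siderosis term.

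| Finding in protocol 9.4.9.4 | MRI parameter in SAP 6.13.7 | Adverse-event comparison in SAP 6.13.2 |
|---|---|---|
| Vasogenic edema | Yes (ARIA-E) | If reported |
| Microhemorrhage | Yes (ARIA-H) | If reported |
| Superficial siderosis | None | If reported |

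**Illustration with assumed rates.** Take new siderosis in 0.5% on placebo and 2% on one dose. Expected cases are 0.005 × n and 0.02 × n; the p-values are two-sided Fisher.

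| Patients per group with both scans | Cases, placebo vs dose | p |
|---|---|---|
| 633 (all randomized) | 3 vs 13 | 0.020 |
| 554 (the plan's completers per arm for 90% power) | 3 vs 11 | 0.056 |
| 475 (1424/3, planned completers) | 2 vs 9, or 2 vs 10 (0.02 × 475 = 9.5) | 0.064 or 0.037 |
| 400 (assumed, after the early stop) | 2 vs 8 | 0.107 |

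The p-value depends on how many patients have both scans and on rounding by a single case. The coverage gap does not.

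**The case against.** **Adverse events will pick it up.** This stands in part. A reader might infer from SAP 6.13.7 that siderosis is never compared between arms. The documents do not support that: symptomatic, clinically significant siderosis should be recorded as an adverse event and enter the Fisher comparisons. Cases without symptoms or not reported remain outside, and adverse-event tables have neither a scan-based denominator nor a split by baseline siderosis.

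**ARIA-H may already include it.** The glossary wording and the SAP category for an increase in size of existing ARIA-H leave some room. The separate listing in 9.4.9.4 and the count categories point the other way. At the least the SAP has to say which is meant.

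**Hemorrhagic findings are still tabulated.** Correct. It would be wrong to infer that the MRI tables could show no hemorrhagic signal at all; microhemorrhage is tabulated and tested by arm. What is missing is a siderosis signal.

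**Macrohemorrhage and infarct.** A reader might extend the point to these. Clinical events already have the stroke cluster in Table AZET.SAP.2 and MACE adjudication (protocol 9.4.9.2). Only silent MRI lesions fall outside, which is secondary.

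**The SAP breaches protocol 10.3.4.** It does not. That sentence is a denominator rule for whichever MRI abnormalities are analyzed.

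**The trial stopped for futility.** SAP 6.1 says no test will be read as statistically significant, which lowers the stakes of any p-value. Safety reporting continues, however: SAP version 3 keeps the MRI comparisons and adds the white-matter shift table.

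**Conclusion.** The point holds in a limited form. SAP 6.13.7 has no superficial-siderosis parameter, although the protocol admits patients with the finding and names it apart from microhemorrhage as a reason to stop treatment. Between-arm comparison is confined to cases reported as adverse events; new or worsened siderosis without symptoms is left out.

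This rests on reading ARIA-H as microhemorrhage, which is the better-supported reading but not the only possible one, and on the SAP's list of MRI parameters being complete. The size is unknown because the documents give no rates; the 3 versus 13 example only shows the kind of difference that would have no row of its own. The consequence is an incomplete safety description, with no bearing on efficacy. The change is worth making because it is small and concerns a finding the protocol itself treats as a safety matter.

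**What to change.** In SAP 6.13.7, state that superficial siderosis is tabulated separately from microhemorrhage, and that the ARIA-H count rows refer to microhemorrhage only. For the Placebo-Controlled period, add by arm:

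- siderosis present or absent at baseline;
- new siderosis, with the denominator limited to patients who have both a baseline and a post-baseline scan and none at baseline;
- worsened siderosis, among patients with both scans who had it at baseline.

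Present each dose beside placebo, either descriptively or with the section's existing chi-square test, using Fisher's exact test where counts are sparse. Take the data from the existing central reads. Rows for silent macrohemorrhage or infarct may be added in the same way but are optional.

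The cost is a few rows in one table. If siderosis was not coded after baseline, the vendor would have to extract it from scans already held. No clinical rule and no study procedure changes.
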